1.1 Scope

This document is a supplement to the BACE-N protocol (ClinicalTrials.gov Identifier: NCT04261309) and comprises a SAP for the article “Modifiable prognostic factors of high cost related to healthcare utilization among older people seeking primary care with a new episode of back pain - an identification and external validation study”. The current SAP has been written while data collection was ongoing (we had access to baseline data, but not to follow-up data) and it will be uploaded to the ClinicalTrials.gov before full access to the study database.

2. Administrative information

Version of SAP

1.0

Study sponsor

Oslo Metropolitan University, the Norwegian Fund for Post-Graduate Training in Physiotherapy and “Et liv i bevegelse” (A life in movement) - Norwegian chiropractors’ research foundation

Names, affiliations and roles of SAP contributors

Name	Title	Affiliation	Role
[name]	[name] University [name] [contact] Email: [contact]	Principal Investigator
[name]	PhD-student	Oslo Metropolitan University	Main author of SAP
[name]	[name] University	Contributor to SAP
[name]	[name]	Contributor to SAP
[name]	[name] MC	Contributor to SAP
[name]	[name] MC	Contributor to SAP
[name] [name]	Erasmus MC	Contributor to SAP
[name]	[name] University	Statistical advisor
[name]	PhD-student	Oslo Metropolitan University	Contributor to SAP
[name]	PhD-student	Oslo Metropolitan University	Contributor to SAP

Signatures: Person writing SAP, senior statistician and chief investigator

[name]

Main author of the SAP

[name]

Senior statistician responsible

[name]

Principal Investigator

3. Study aim

The aim of this study is 1) to identify modifiable prognostic factors for high costs related to healthcare utilization among older people seeking primary care with a new episode of back pain and 2) to replicate the identified associations of modifiable prognostic factors in a similar cohort of older back pain patients.

4. Study design, population and method

Study design

This study will be carried out in two steps. First, modifiable prognostic factors will be identified in a prospective observational cohort study with one year of follow-up within a Norwegian primary care setting (the BACE-N). Next, a replication analysis of identified prognostic factors will be conducted in a prospective observational cohort study within a Dutch primary care setting (the BACE-D).

The BACE-N and the BACE-D studies are part of the international BACE consortium [1]. The BACE-N study (ClinicalTrials.gov Identifier: NCT04261309) was classified as a quality assessment study by the Norwegian Regional Committee for medical Research Ethics (reference no. 2014/1634/REK vest) and approved by the Norwegian Social Science Data Service (reference no. 42149) in 2015.

Study population and recruitment

BACE-N: Eligible patients are people 55 years of age or older who seek primary care (physiotherapist, chiropractor or GP) with a new episode of back pain (preceded by 6 months without visiting a primary care provider for similar complaints). Patients are excluded if they have difficulties completing the questionnaires (e.g. unable to speak, read or write in Norwegian) or if they have difficulties completing the physical examination (e.g. are wheelchair bound). Patients are recruited from physiotherapist, chiropractors and GPs working in Norwegian primary care between April 2015 and February 2020. Patients who meet the eligibility criteria and complete the consent to participate are included in the study.

BACE-D: Eligible patients were people over 55 years of age (n=675) who sought primary care (GPs) with a new episode of back pain (preceded by 6 months without visiting a primary care provider for similar complaints). Patients were excluded if they had difficulties completing the questionnaires (e.g. unable to speak, read or write in Dutch) or if they had difficulties completing the physical examination (e.g. are wheelchair bound). Patients were recruited from GPs working in Dutch primary care between March 2009 and September 2011. Patients who meet the eligibility criteria and complete the consent to participate were included in the study.

Method

BACE-N: At baseline all patients responded to a comprehensive questionnaire and went through a standardized physical examination conducted by local research assistants at test

SAP Modifiable prognostic factors of high cost related to healthcare utilization among older people seeking primary care with a new episode of back pain - an identification and replication study (working title)

stations established within each recruiting area. Follow-up questionnaires will be sent at 3, 6, and 12 months after inclusion for completion at home. All questionnaires are preferably completed electronically using the Infopad system, but paper versions will be available for patients not familiar with electronic data collection. All information will be stored and analysed securely through Service for sensitive data (TSD) at the University of Oslo, Norway.

BACE-D: At baseline all patients responded to a comprehensive questionnaire and went through a standardized physical examination. Follow-up questionnaires were sent (by e-mail or postal) at 3, 6, 9 and 12 months after inclusion.

Variables

Outcome variable

The outcome of this study is costs related to healthcare utilization aggregated for one year of follow up and dichotomized as high and low. Having high costs related to healthcare utilization is defined as patients with costs in the top 25th percentile [2, 3].

Healthcare utilization within the BACE-N and the BACE-D will be self-reported and include; consultation to healthcare professionals (type and frequency), number of diagnostic examinations (type and frequency), number of days of hospitalization and/or institutionalisation (only included in the BACE-N), back operations and use of back medication (both prescription and over-the-counter, type and frequency). All variables, except back operations, will be reported with a 3 month recall period at 3, 6, and 12 months follow-up for the BACE-N, at 3, 6, 9, and 12 months follow-up for the BACE-D. Back operations will be reported with a 12 month recall period at 12 months follow-up.

Healthcare utilization during the one year of follow-up will be described as shown in table 3 (BACE-N and BACE-D). The total cost of healthcare utilization will be estimated based on information presented in table 3 and unit costs of healthcare resources collected from national pricelists in Norway and the Nederlands (see table 1).

Potential modifiable prognostic factors

Potential modifiable prognostic factors are factors expected to have the potential to be modified *through healthcare system encounters* and therefore classified as modifiable. Potential modifiable prognostic factors of high-costs related to healthcare utilization are based on previous literature and will be measured at baseline.

- Pain severity [2-7] measured by the NRS
- Disability [2-6, 8] measured by the RMDQ
- Health-related quality of life [6, 7] measured by the SF36 using the physical and mental summary score
- Emotional well-being [2, 3, 8-10] measured by the CES-D
- Kinesiophobia [3, 10] measured by the FABQ-PA
- Comorbidity [11] measured by the SCQ
- Radiating pain below the knee [3] measured by the question “did your back pain radiate to your legs last week? If yes, how far down did the pain radiate last week?” categorized into yes or no

- Expectations of recovery measured with a five-point scale

The Numeric Rating Scale (NRS) will be used to measure average pain severity last week [12]. The NRS, scored from 0 (no pain) to 10 (maximum pain), has been widely used to evaluate pain and has proven to be preferable when examining low back pain patients [13], also for Norwegian patients [14].

The Roland Morris Disability Questionnaire (RMDQ) [15] will be used to measure disability. The RMDQ is a widely used back-specific patient-reported measure of pain-related disability (0 = no disability, 24 = totally disabled). The Norwegian version has been validated and found to have good measurement properties when used among patients with low back pain [14, 16].

The Short Form-36 Health Status Questionnaire (SF36) [17] will be used to assess health-related quality of life. The SF36 consist of 36 items. It measures health on eight multi-item dimensions, covering physical functioning, social functioning, role limitations (physical problems), role limitations (emotional problems), mental health, vitality, pain, and overall evaluation of health [17]. Data-completeness of the SF36 in the general population in Norway seems to strongly declined with increasing age [18]. Hence, caution should be exercised when assessing subjective health or employing the norms among subjects aged 70 years or over [18].

The Center for Epidemiologic Studies Depression Scale (CES-D) will be used to assess emotional well-being. The CES-D has been widely used in studies of late-life depression. Psychometric properties are generally favourable [19]. The Norwegian version of the CES-D has been used among older patients in order to measure depression symptoms [20].

The Fear Avoidance Beliefs Questionnaire, physical activity subscale (FABQ-PA) [21] will be used to assess kinesiophobia. The FABQ-PA consists of four questions aimed towards physical activity, scored on a 7-point ordinal scale, which are summed up to a sum score, ranging from 0 (no fear) to 24 (maximum fear). The questionnaire has been translated into Norwegian and has shown acceptable psychometric properties in Norwegian patients with low back pain [22].

The Self-Administered Comorbidity Questionnaire (SCQ) [23] will be used to assess comorbidity. The SCQ is a 14-item measure of comorbidity for clinical and health services research settings. An individual can receive a maximum of 3 points for each medical condition: 1 point for the presence of the problem, another point if he/she receives treatment for it, and an additional point if the problem causes a limitation in functioning. Because there are 12 defined medical problems and 3 optional conditions, the maximum score totals 45 points if the open-ended items are used and 36 points if only the close-ended items are used.

Potential covariates

Potential covariates will be included in the analyses based on previous literature and will be measured at baseline.

- Sex [4-6, 24, 25]

- Age [4, 6, 24, 25]
- Education level [8, 26] measured as the highest education completed, categorised into high vs low (low consists of up to high school and occupational high school)
- Employment status measured by the question “do you have a paying job?” categorized into yes or no
- Pain duration [2] measured by the question “how many days have you had your current back pain?”
- Pain history [5] measured by the question “have you had back pain before?” categorized into yes or no
- First healthcare provider [27]
- Costs related to healthcare utilization prior to inclusion

Healthcare utilization prior to inclusion will be measured (with variables as described above) at baseline, in the period from baseline to 6 and 12 weeks retrospectively, for the BACE-N and the BACE-D study respectively. The total cost of healthcare utilization will be estimated as described above.

Other variables

Included patients (BACE-N and BACE-D) will be described with respect to the following baseline characteristics: ethnicity, pain location and healthcare utilization prior to inclusion (see table 2). In addition, we have included the following potential prognostic factors and covariates (as described above): age, gender, educational level, employment status, first healthcare provider, pain severity, pain duration, pain history, disability, health-related quality of life, emotional well-being, kinesiophobia, expectation of recovery and comorbidity.

5. Statistical analyses

General analysis considerations

All analyses described in this plan are considered a priori in that they have been defined in the protocol and/or in this SAP. All post hoc analyses will be identified as such in the article if relevant. All analyses will be carried out by a PhD-student using SPSS version 26 and controlled by a senior researcher/statistician. All statistical tests will be two-sided, and nominal p-values will be reported. All confidence intervals will be reported as 95%.

Preliminary analyses assessing the influence of missing data and assumptions of normality for continuous variables will be conducted. The assumption of normal distribution will be investigated using histograms and QQ-plots. Normally distributed data will be presented with means and standard deviations (SDs), skewed data with medians and interquartile range (IQR). Categorical data will be reported as counts and percentages. Missing data will be handled by multiple imputation, using 5 imputations and 10 iterations unless the missingness exceeds 30% and missing at random cannot be assumed. Fully conditioned specification method and regression estimation will be used. For variables where we are unable to use regression estimation due to computational difficulties, predictive mean matching will be used [28].

Description of study flow

The flow of participants through the study will be reported according to the STROBE guidelines [29] with a flow chart (see figure 1). Reasons for dropout will be provided where known. Differences between responders and non-responders will be evaluated.

Participant characteristics

Baseline characteristics of included patients will be presented as shown in table 2.

Preparatory analysis

First, type and frequency of use of different healthcare resources will be calculated for each of the follow-up periods; from baseline to 3 months, 3 to 6 months, and 9 to 12 months for the BACE-N study, and from baseline to 3 months, 3 to 6 months, 6 to 9 months, and 9 to 12 months for the BACE-D. Healthcare utilization will be presented as shown in table 3.

Next, costs will be estimated based on information presented in table 3, and unit costs of healthcare resources collected from national pricelists in Norway and the Nederlands (see table 1). Costs related to back medication will be estimated based on medication type (not exact medication name) and frequency of use. Data on dosage is not available. All costs will be presented in Euros (€) 2020. Costs of healthcare utilization will be described with median and interquartile range for the entire follow-up period as shown in table 4.

Identification analysis

Univariable and multivariable binary logistic regression models will be used to investigate individual association (crude and adjusted for selected covariates) between each predefined prognostic factor and costs related to healthcare utilization (within the BACE-N). The cost score will be entered into the model as a dependent dichotomous variable (high cost defined as patients with cost in the top 25th percentile, yes/no). The results will be presented as crude and adjusted odds ratios (OR) with 95% confidence intervals (CI) as shown in table 5.

Replication analysis

Univariable and multivariable binary logistic regression models will be used, as described above, to replicate findings from the identification analysis within the BACE-D material. The results will be presented as crude and adjusted odds ratios (OR) with 95% confidence intervals (CI) as shown in table 5. The decision on whether findings are replicated will be based on the size and direction of the association, the confidence interval and the p-value for each of the predefined prognostic factors [30].

Sample size

This study contains secondary analyses embedded in the BACE-N and the BACE-D study. Details on sample size calculation are provided in the BACE-N (ClinicalTrials.gov Identifier: NCT04261309) and the BACE-D protocol [1].

To determine statistical power of this study we used number of events per variable (EPV) [46-50] and the rule-of-thumb of “10 events per 1 analysed variable” [51-54]. With a sample size of 450 participants within the BACE-N study, we anticipate 112 participants to be in the top 25th percentile of costs due to healthcare utilization and categorised as having high costs (yes/no) due to healthcare utilization (events). An EPV of 10 will allow a maximum of 11 prognostic variables to be included in

SAP Modifiable prognostic factors of high cost related to healthcare utilization among older people seeking primary care with a new episode of back pain - an identification and replication study (working title)

the final multivariable prediction model. With a sample size of 675 participants in the BACE-D, we anticipate 168 participants to be in the top 25th percentile of costs due to healthcare utilization and defined as having high costs (yes/no) due to healthcare utilization (events). An EPV of 10 will allow a maximum of 16 prognostic variables to be included in the final multiple prediction model.

[Sensitivity analysis](#)

To assess the robustness of the results complete case analysis (without using imputation for missing data) will be carried out as a sensitivity analysis.

6. Selection bias, information bias and covariates

[Selection bias:](#)

Because of limited resources and practical reasons related to recruitment from a broad network of clinicians, the BACE-N and the BACE-D lacks information on eligible study participants that declined to participate or for other reasons were not invited. In order to assess representativeness, the BACE-N study sample will be compared on key sociodemographic variables with a sample from the longitudinal population study of people in the second half of life; The Norwegian study on life course, ageing and generation (NORLAG). The NORLAG study is expected to represent a representative sample of older people with musculoskeletal complaints.

Response rate at each assessment point and reasons for loss to follow-up will be reported. Key baseline characteristics will be compared between those lost to follow-up and those remaining in the study.

[Information bias:](#)

To reduce the risk of information bias, the study outcome (costs) will be measured in an identical manner in all included cases, and in the best possible way within the framework of the BACE-N and the BACE-D study.

[Covariates:](#)

Covariates may influence associations between prognostic factors and outcome. Therefore, in line with the PROGRESS framework and recommendations for type 2 studies [31], we will adjust for covariates when evaluating prognostic factors.

Table 1 Cost categories, units, unit price, all numbers in Euros (€) for 2020?

Cost categories	Unit	Norwegian unit price (€)	Dutch unit price (€)	Reference (source)
Primary care				
General practitioner	Per visit			
Medical specialist	Per visit			
Occupational physician	Per visit			
Physiotherapist	Per visit			
Chiropractor	Per visit			
Manuel therapist	Per visit			
Naprapath	Per visit			
Osteopath	Per visit			
Psychologist	Per visit			
Other therapists	Per visit			
Back medication				
Paracetamol	Per daily defined dose			
NSAID	Per daily defined dose			
Muscle relaxant	Per daily defined dose			
Sleep medication	Per daily defined dose			
Cortisone	Per daily defined dose			
Opioid	Per daily defined dose			
Antidepressant	Per daily defined dose			
Anticonvulsant	Per daily defined dose			
Others	Per daily defined dose			
Examinations				
Blood sample	Per examination			
X-ray	Per examination			
MRI	Per examination			
CT	Per examination			
Others??	Per examination			
Secondary care				
Back operation	Per operation			
Hospitalization (non-operation)	Per day			
Rehabilitation stay	Per day			

NoMA, Norwegian Medicines Agency

SAP Modifiable prognostic factors of high cost related to healthcare utilization among older people seeking primary care with a new episode of back pain - an identification and replication study (working title)

Table 2 Patient characteristics and clinical status at baseline

	BACE-N (n = x)	BACE-D (n = x)
Female, N (%)		
Age in years, mean (SD)		
Education level high, N (%)		
Ethnicity Norwegian (BACE-N) or Dutch (BACE-D), N (%)		
Employment status, N (%)		
Currently paid work		
First healthcare provider, N (%)		
General practitioner		
Physiotherapist		
Chiropractor		
Pain location, N (%)		
Lumbar		
Thoracic		
Radiating pain below the knee		
Average pain severity last week (NRS 0-10), median (IQR)		
Pain duration, N (%)		
< 6 weeks		
6 weeks to 3 months		
> 3 months		
Previous episodes of back pain, N (%)		
Disability (RMDQ 0-24), mean (SD)		
Comorbidity (SCQ, 0-15)		
Health-related QOL (SF36, 0-100), mean (SD)		
Physical component		
Mental component		
Emotional well-being (CES-D 0-60)		
Kinesiophobia (FABQ-PA 0-24)		
Expectation of recovery within 3 months, N (%)		
Fully recovered		
Much better		
No change or worse		
Healthcare utilization prior to inclusion		
Patients with primary care consultation last 6 (BACE-N) or 12 (BACE-D) weeks, N (%)		
General practitioner		
Medical specialist		
Occupational physician		
Physiotherapist		
Chiropractor		
Manual therapist		
Naprapath		
Psychologist		
Other therapists		
Patients with use of back medication, N (%)?		
Patients with diagnostic examination last 6 (BACE-N) or 3 (BACE-D) months, N (%)		
Blood sample		
X-ray		
MRI/CT scan		
Patients with previous hospitalization, N (%)		
Patients with previous rehabilitation stay, N (%)		

NRS indicates Numeric Rating Scale; RMDQ, The Roland Morris Disability Questionnaire; SCQ, The Self-Administered Comorbidity Questionnaire; SF-36, 36-Item Short-Form Health Survey; CES-D, The Center for Epidemiologic Studies Depression Scale; FABQ-PA, The Fear Avoidance Beliefs Questionnaire, physical activity subscale.

SAP Modifiable prognostic factors of high cost related to healthcare utilization among older people seeking primary care with a new episode of back pain - an identification and replication study (working title)

Table 3 Healthcare utilization throughout one-year of follow-up

	BACE-N			BACE-D			
	0-3 months	>3-6 months	>9-12 months	0-3 months	>3-6 months	>6-9 months	>9-12 months
Primary care							
Patients with primary care consultation, N (%)							
General practitioner							
Medical specialist							
Occupational physician							
Physiotherapist							
Chiropractor							
Manual therapist							
Naprapath							
Psychologist							
Other therapists							
No. of general practitioner consultations, median (IQR)							
No. of medical specialist consultations, median (IQR)							
No. of occupational physician consultations, median (IQR)							
No. of physiotherapist consultations, median (IQR)							
No. of chiropractor consultations, median (IQR)							
No. of manual therapist consultations, median (IQR)							
No. of naprapath consultations, median (IQR)							
No. of psychologist consultations, median (IQR)							
No. of other consultations, median (IQR)							
Back medication							
Patients with use of back medication, N (%)							
Paracetamol							
NSAID							
Muscle relaxants							
Sleep medication							
Cortisone							
Opioid							
Others							
Frequency of use paracetamol, N (%)							
Daily							
Weekly							
Monthly or less							
Frequency of use NSAID, cortisone N (%)							
Daily							
Weekly							
Monthly or less							
Frequency of use muscle relaxants, sleep medication, N (%)							
Daily							
Weekly							
Monthly or less							
Examinations							
Patients with additional diagnostic examination, N (%)							
Blood sample							
X-ray							
MRI/CT scan							
Others							
Secondary care							
Patients with back operation, N (%)							
Patients with hospitalization, N (%)							
Duration of stay in days, median (IQR)							
Patients with rehabilitation stay, N (%)							
Duration of stay in days, median (IQR)							

SAP Modifiable prognostic factors of high cost related to healthcare utilization among older people seeking primary care with a new episode of back pain - an identification and replication study (working title)

Table 4 Cost related to healthcare utilization from 0-12 month*

	BACE-N	BACE-D
Primary care		
General practitioner		
Medical specialist		
Occupational physician		
Physiotherapist		
Chiropractor		
Manual therapist		
Naprapath		
Psychologist		
Other therapists		
Back medication		
Paracetamol		
NSAID, cortisone		
Muscle relaxants, sleep medication		
Examinations		
Blood sample		
X-ray		
MRI		
CT		
Others		
Secondary care		
Back operation		
Hospitalization and/or rehabilitation stay		
Total costs		

Values are median (interquartile range) of costs (€). *Cost related to healthcare utilization for the entire follow-up period is calculated on basis of the three (BACE-N) and four (BACE-D) follow-up periods

Table 5 Binary logistic regression analyses; individual associations between modifiable prognostic factors and high costs related to healthcare utilization (dependent variable)

	BACE-N		BACE-D	
	Crude OR (95% CI)	Adjusted OR* (95% CI)	Crude OR (95% CI)	Adjusted OR* (95% CI)
Pain severity (NRS, 0-10)				
Disability (RMDQ, 0-24)				
Health-related QOL (SF36, 0-100)				
Physical component				
Mental component				
Emotional well-being (CES-D 0-60)				
Kinesiophobia (FABQ-PA 0-24)				
Comorbidity (SCQ, 0-15)				
Radiating pain below the knee				
Yes				
No				
Expectation of recovery within 3 months, N (%)				

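### In the prognostic-factor SAP, inpatient days enter the high-cost outcome for BACE-N only, and no planned analysis separates non-replication in BACE-D from a difference in outcome composition

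*Combined protocol and SAP*

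**What the plan says.** All references are to the SAP on modifiable prognostic factors of high cost (11.03.2021) unless stated otherwise.

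- **Definition of the outcome (section 4).** It reads: "The outcome of this study is costs related to healthcare utilization aggregated for one year of follow up and dichotomized as high and low". The cut-off is: "Having high costs related to healthcare utilization is defined as patients with costs in the top 25th percentile". The event counts under Sample size apply it within each cohort.
- **Components (same section).** Consultations, diagnostic examinations, back operations and back medication are listed for both cohorts. Inpatient days carry a restriction: "number of days of hospitalization and/or institutionalisation (only included in the BACE-N), back operations and use of back medication".
- **Construction of the total.** "The total cost of healthcare utilization will be estimated based on information presented in table 3", multiplied by Norwegian or Dutch unit prices from Table 1.
- **Tables.** Table 1 has a Dutch price column against hospitalisation and rehabilitation stay, both priced per day, and its hospitalisation row excludes operations. Table 3 has hospitalisation and rehabilitation rows under BACE-D. Table 4 has a cost row, "Hospitalization and/or rehabilitation stay", under both cohorts. No cell is marked as unavailable for BACE-D.
- **Replication (section 5).** It is planned thus: "Univariable and multivariable binary logistic regression models will be used, as described above, to replicate findings from the identification analysis within the BACE-D material". Judgement rests on size, direction, confidence interval and p-value for each factor, without a numerical rule.
- **Sensitivity analysis (section 5).** Complete case only.
- **Information bias (section 6).** The SAP states that "the study outcome (costs) will be measured in an identical manner in all included cases", followed by a clause limiting this to what the two studies allow.

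**The concern.** Replicating the identified associations is one of the SAP's two aims. It is assessed by setting BACE-N and BACE-D odds ratios next to each other in Table 5. That comparison is clean only if the dependent variable means the same thing in both columns.

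As the outcome section is written, a BACE-N patient can be classed as high cost because of a non-operative hospital or rehabilitation stay. A BACE-D patient with the same history would be ranked without it. A factor related to admission could then show a larger odds ratio in BACE-N than in BACE-D. A factor unrelated to admission could show a smaller one. Either difference could be read as a finding about the factor.

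The mismatch may also reach the adjusted models. Prior healthcare use is to be measured with the same variables and costed in the same way, and prior cost is an adjustment covariate under Table 5. The SAP does not say whether the restriction on inpatient days applies there too, and Table 2 lists previous hospitalisation and rehabilitation stay under both cohorts.

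**Working it through.** **1. The plan's own counts.** Events are 25% of N, rounded down, and the variable limit is events / 10, rounded down.

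- BACE-N: 0.25 × 450 = 112.5, so 112 events and 11 variables.
- BACE-D: 0.25 × 675 = 168.75, so 168 events and 16 variables.

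Both match the Sample size section. A top-quartile rule fixes these counts whatever the components. Composition changes which patients are events, not how many.

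**2. Which cost is unmatched.** Back operations are costed in both cohorts, and Table 1 prices only hospitalisation without an operation per day. The unmatched part is therefore non-operative hospital days and institution or rehabilitation days. I take the institutionalisation of the text and the rehabilitation stay of the tables to be the same item.

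**3. How many BACE-N events could depend on it.** The documents give no inpatient rate, so the rate h is an assumption. Suppose that every stay is costly enough to put the patient in the top quartile, and that admission is independent of other costs. Then 25% of admitted patients are high cost anyway and 75% are newly moved in, each displacing another patient.

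Events changed = 0.75 × h × 450. Share of events = 0.75h / 0.25 = 3h.

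| Assumed h | Patients with a stay (450h) | Events changed | Share of events |
|---|---|---|---|
| 2% | 9 | 6.75 | 6% |
| 5% | 22.5 | 16.9 | 15% |
| 8% | 36 | 27 | 24% |

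These are ceilings under independence. They fall if some stays are too cheap to reach the quartile, or if admitted patients also use more of the other services.

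**4. What this could do to an odds ratio.** A simulation (400,000 patients, lognormal other costs, each stay dominating other costs) started from a crude odds ratio of about 1.40 per SD of a factor when inpatient days are left out. Adding inpatient days gave:

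| Assumed h | Factor unrelated to admission | Weakly related (log odds 0.2 per SD) | Strongly related (log odds 0.7 per SD) |
|---|---|---|---|
| 1% | 1.40 | 1.41 | 1.43 |
| 5% | 1.35 | 1.38 | 1.54 |
| 10% | 1.26 | 1.38 | 1.68 |

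The shift can go either way. It is at most about 0.03 at a 1% rate.

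**5. Scale against sampling error.** With 450 patients and a 25% event share, the standard error of a log odds ratio per SD is roughly 1/√(450 × 0.25 × 0.75) = 1/√84.4 = 0.109. For an odds ratio of 1.40, the 95% interval is about 1.13 to 1.73. All the simulated values lie inside it. The composition effect is systematic, but under these assumptions it is no larger than the sampling uncertainty of a single BACE-N estimate.

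**The case against.** The strongest reply is that this is a disclosed and partial mismatch, imposed by re-using an earlier cohort. Most components are shared, operation costs are counted in both cohorts, and the simulated shifts sit within the confidence interval. Other differences remain whatever is done here: BACE-N has no 6 to 9 month recall window, so it covers 9 of 12 months for recalled items against 12 of 12 in BACE-D, and prices are national. Dropping inpatient days also narrows what high cost means. All of this is correct. It limits the size of the problem and what harmonisation can achieve. It does not supply an analysis that would show whether composition mattered.

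Four stronger readings are tempting, and the documents do not support them.

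- A reader might infer that BACE-D never collected inpatient days. The outcome section says only that they are included in BACE-N. Non-collection is the likelier reading, but the rows in Tables 1 to 4 point the other way.
- A reader might infer that the information-bias sentence falsely claims identical measurement across cohorts. It is qualified by its closing clause, and almost the same sentence stands in the SAP on healthcare utilization and related cost, which has a single cohort. It can be read as referring to patients, not cohorts.
- A reader might put the ceiling at 8%, 20% or 32% of events for rates of 2%, 5% or 8%, by assuming that no admitted patient would otherwise be high cost. Under independence a quarter would be.
- A reader might conclude that no replication result can be attributed to the factor. With most components shared, agreement despite a partly different outcome would be some evidence of robustness.

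**Conclusion.** The point holds in a limited form. The outcome section and Tables 1, 3 and 4 disagree on whether BACE-D has inpatient days and must be reconciled. If BACE-D lacks them, the same outcome label rests on different components in the two cohorts, and the plan contains no analysis that could tell a factor that fails to replicate from a component that is missing.

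The size cannot be settled from the documents. It depends on an inpatient rate that they do not give, on how often a stay alone is enough to reach the top quartile, and on how each factor relates to admission. With few admissions the effect is negligible. At 5% or more it could visibly move an odds ratio. Because the rate is not given, the comparison should be specified in advance. The planned counts of 112 and 168 events are unaffected.

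**What to change.** 1. State whether BACE-D has non-operative hospital and rehabilitation days. If it does, remove the restriction in the outcome section and cost them in both cohorts. If it does not, mark the BACE-D cells in Tables 1, 3 and 4 as not available and take the steps below.
2. Pre-specify a common-component cost without non-operative hospital and rehabilitation days. Re-derive the BACE-N top quartile on it, run the BACE-N crude and adjusted models on it, and use those odds ratios against BACE-D when judging replication.
3. Report the all-component BACE-N outcome alongside and state whether conclusions differ. It should not be the sole identification result, because factors identified on one outcome would then be judged on another.
4. Build the prior-cost covariate from the same components in both cohorts.
5. Qualify the information-bias sentence so that it does not suggest identical costing across cohorts.
6. List the missing BACE-N 6 to 9 month window and the national prices as remaining limitations.

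The cost is SAP wording and one extra set of BACE-N logistic models on data already collected. The downside is a narrower cost construct for the replication comparison.
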